5.11.4. RISKS ASSOCIATED WITH STUDY PARTICIPATION

Subjects enrolled in the study will receive treatment with commercially-available devices and equipment per the site's standard-of-care. The investigational system will function independently from the commercially-available devices. Therefore, there is no risk that the investigational system will affect the functionality of the commercially-available devices.

Since all subjects enrolled in the study are required to undergo intracardiac echocardiography with the VERAFEYE System, the total procedure duration is likely to increase compared to a procedure without intracardiac echocardiography. Care will be taken to limit any potential increase in procedure time, and the total procedure time is expected to continue to be in line with standard of care intracardiac echocardiography cases. There is no increased risk for serious injury due to the potential increased procedure time.

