5.10.3.3. Procedure Workflows**Pre-Procedural Imaging**

Pre-procedural imaging will be performed per hospital standard of care to assess the anatomy and to exclude the presence of thrombus. If an intracardiac thrombus is visualized, the procedure will be aborted and the subject will be withdrawn from the study. Pre-procedural imaging may be collected at baseline or on the day of the procedure.

Intra-Procedural Imaging

VERAFEYE imaging data from the right atrium will be obtained during the ablation, or LAA/ASD closure procedure. This procedure is to be performed using a commercially available ablation catheter or LAA/ASD closure device. The choice of the ablation catheter, or LAA/ASD closure device is at the operator's discretion. This ablation, or LAA/ASD closure procedure will be performed according to standard of care. The ablation, or LAA/ASD closure procedure will not be guided by the data collected from the VERAFEYE System, the physician is to adhere to a standard workflow and rely on standard imaging and diagnostic tools, as applicable. In order to prevent artifact between the VERAFEYE System and the standard of care echocardiography imaging (intracardiac echocardiography (ICE) transesophageal echocardiography (TEE)), the VERAFEYE imaging has to be frozen during standard of care echocardiography imaging and vice versa.

No concomitant procedures are allowed to be performed at the time of the ablation, or LAA/ASD closure procedure under this protocol. It is also not allowed to combine an ablation procedure with an LAA/ASD closure procedure or to combine an LAA closure procedure with an ASD closure procedure.

It is recommended that the following views with the VERAFEYE Imaging Catheter be obtained in order to visualize the major anatomical structures, as well as third party devices.

RA (typical AFL) Ablation

- Home view
- A variety of anatomical views from different VERAFEYE Imaging Catheter locations, at the discretion of the investigator
- View to visualize mapping* and/or ablation catheter

*If used, per hospital standard's of care

**LUMINIZE_CLINICAL PROTOCOL**Document ID: VER-DOC-527
Controlled Document: VER-SIGN-3084TEMPLATE:
ONEPROJECTS/SIGN-267

Version: 4.0

Project: VERAFYE (VER)
Date: 22-Nov-2024 14:16:10
Page: 26 / 51**LA (AF) Ablation**

- Home view
- A variety of anatomical views from different VERAFYE Imaging Catheter locations, at the discretion of the investigator
- Transseptal puncture view

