5.11.2. RISKS ASSOCIATED WITH THE STUDY DEVICE

The risks associated with use of the VERAFYE System are not substantially or incrementally different from commercially available and widely used ICE systems for cardiac EP or LAA/ASD closure procedures. The below list of potential adverse effects associated with the use of this device and other devices in this field is widely known and understood when considering usage of ICE in EP or LAA/ASD closure procedures.

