5.11.5. BENEFITS ASSOCIATED WITH STUDY PARTICIPATION

The VERAFEYE System is similar in technology and indication to existing commercially available ICE systems, such as UltraICE (Boston Scientific), AcuNav and Soundstar (Biosense Webster), ViewFlex (Abbott). ICE systems provide the operator with additional means of intra-operative guidance such as orientation within the heart, and evaluating the size of the lumens. While there may be no direct benefit from participating in this study, because the VERAFEYE System provides real-time imaging, complications may potentially be detected earlier on.

**LUMINIZE_CLINICAL PROTOCOL**Document ID: VER-DOC-527
Controlled Document: VER-SIGN-3084TEMPLATE:
ONEPROJECTS/SIGN-267

Version: 4.0

Project: VERAFEYE (VER)
Date: 22-Nov-2024 14:16:10
Page: 34 / 51

The data collected in this clinical investigation will serve as critical input for VERAFEYE imaging technology improvement, as well as for the novel features development in future device releases. In this regard, the proposed clinical investigation is a pivotal step toward the development of next-generation intraoperative 4D-imaging devices, aimed to improve outcomes for future patients undergoing catheter ablation and structural heart procedures.

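### Does the no-risk statement in Section 5.11.4 conflict with the freezing rule for standard echo in Section 5.10.3.3?

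*Combined protocol and SAP*

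**What the plan says.** Section 5.11.4 argues in three steps. Subjects "will receive treatment with commercially-available devices and equipment" under the site's usual care. Next, "The investigational system will function independently from the commercially-available devices". From this it concludes that "there is no risk that the investigational system will affect the functionality of the commercially-available devices". The section also accepts that the procedure will probably take longer than one without intracardiac echo, and says that "Care will be taken to limit any potential increase in procedure time".

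Section 5.10.3.3, on imaging during the procedure, sets a rule. "In order to prevent artifact between the VERAFEYE System and the standard of care echocardiography imaging" (it names ICE and TEE), "the VERAFEYE imaging has to be frozen during standard of care echocardiography imaging and vice versa". The same paragraph says that the ablation catheter or closure device is a commercial product, that the operator keeps to the usual workflow and usual imaging tools, and that VERAFEYE data do not guide the treatment.

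Later in 5.10.3.3, the VERAFEYE catheter (VIC) is the last catheter to come out, and optional imaging of the pericardial space is allowed once only the VIC remains. Section 5.10.3.4 records total procedure time (first sheath in to last catheter out) and VIC in-body time (VIC in to VIC out).

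Section 5.6 sets no formal endpoints, and Section 5.12 plans descriptive analysis only.

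**The concern.** Two systems that must take turns are not independent in use. Section 5.10.3.3 treats artifact as real enough to need a binding rule, and the rule works in both directions, so standard echo also stops while VERAFEYE images. Section 5.11.4 mentions neither the artifact nor the freezing and draws an absolute conclusion from independence alone. It is the section on risks of taking part, in a protocol that an ethics committee reviews. An absolute safety statement resting on a reason that the workflow section undercuts could leave a reader with too favourable a view.

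The timing point looks like a lost measurement. If both recorded durations end when the VIC comes out, neither shows how long the VIC stayed in after everything else was removed. That interval is time with only the study catheter in place, in a protocol that promises to limit added time.

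**Working it through.** The main point involves no figure, and the protocol has no power or sample-size calculation that bears on it. The check is a comparison of texts, followed by simple algebra for the times.

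**1. What the commercial label covers**

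| Section | What is called commercial | Role there |
|---|---|---|
| 5.10.3.3 | Ablation catheter, LAA/ASD closure device | Used on the subject |
| 5.11.4, first sentence | Devices and equipment | Used to treat the subject |
| 5.11.4, independence and no-risk sentences | Devices only | Used on the subject |
| 5.11.2 | ICE systems: "not substantially or incrementally different from commercially available and widely used ICE systems" | Market comparator |
| 5.11.5 | ICE systems: "similar in technology and indication to existing commercially available ICE systems" | Market comparator |

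Where the workflow is set out, the label goes to the treatment devices, and echo is named as standard of care. Sections 5.11.2 and 5.11.5 do call ICE systems commercial, but as products to compare VERAFEYE with. The word that could bring echo into 5.11.4 is *equipment*, and it does not recur in the two sentences that matter.

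**2. Consequence under each reading**

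- *Treatment devices only.* The freezing rule concerns other equipment, and the two sections do not conflict.
- *Echo included.* The independence argument fails for echo. What limits artifact is the freezing rule, which 5.11.4 does not mention.

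Under both readings the operator freezes one system while the other images, the same data are recorded and the same descriptive summaries are produced.

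**3. The recorded times**

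Let S = first sheath in, I = VIC in, T = last third-party catheter out, R = VIC out. Because the VIC comes out last, R is also the last catheter removal.

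- Total procedure time = R − S
- VIC in-body time = R − I
- Difference = (R − S) − (R − I) = I − S
- VIC-only interval = R − T

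T appears in neither recorded time, so R − T cannot be derived from them. If T is not before I, then R − T lies between 0 and R − I.

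The documents give no minutes. With assumed values S = 0, I = 10 and R = 90, the recorded times are 90 − 0 = 90 and 90 − 10 = 80. They are the same whether T = 88 (VIC-only 90 − 88 = 2) or T = 60 (VIC-only 90 − 60 = 30); the possible range is 0 to 80. This illustrates the algebra and says nothing about typical durations in this study.

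**4. Whether R − T is needed**

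The objective in Section 5.5 is usability and integration. Nothing in Sections 5.5, 5.6 or 5.12 calls for the VIC-only interval. Nor would it measure the added procedure time discussed in 5.11.4: it leaves out VERAFEYE imaging and freezing during the treatment itself, and a single-arm study has no comparison procedure without the device. The printed lab procedure report listed in Section 5.15.2 may already carry the removal time.

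**The case for a change.** The best case for acting has four parts. First, the opening sentence of 5.11.4 speaks of equipment as well as devices and does not exclude echo, while nearby sections call ICE systems commercial. Second, if freezing keeps the risk down, then freezing is the reason, and a risk held down by an operator-dependent control should be described with that control. Third, clean images are what an imaging device is for, so artifact does bear on its functionality. Fourth, standard echo is among the tools the operator relies on, and the rule stops it while VERAFEYE images.

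Much of this stands. The wording is more absolute than its stated reason supports if echo is included, and the scope is not spelled out. What does not stand is a firm contradiction, because the protocol's own usage in 5.10.3.3 supports the narrower reading. It also does not follow that anything is hidden or uncontrolled: the artifact and its control are stated openly as a requirement in the same document, and operators must be trained on that protocol (Section 5.10.3.1). The documents report no malfunction or harm to a standard system, and they do not show how often, if ever, needed echo is displaced.

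On the times, the algebra stands. A shared end point between two clearly defined durations is not an error, and an additional derived variable would be a preference.

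**Conclusion.** No change to the plan follows. The main point is an unclear scope in two sentences of 5.11.4, set against one explicit rule in 5.10.3.3. If echo is meant to be covered, the independence argument is wrong for echo, and the two sections would need to be reconciled in wording. A scope word and a cross-reference could be added whenever 5.11.4 is next opened for another reason. That would alter no conduct, data or result, and an amendment for it alone, with the ethics review that Section 5.14.9 requires, would gain nothing. The VIC-only interval cannot be recovered from the two listed times, but nothing planned depends on it.

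This rests on three assumptions: the freezing rule is followed as written; the VIC is the last catheter out, as 5.10.3.3 says; and no planned summary outside these documents uses the VIC-only interval. The consent form, Investigator Brochure and instructions for use were not available, so whether they describe the artifact and freezing is unknown. No view is taken on the clinical workflow itself.

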5.11.5. BENEFITS ASSOCIATED WITH STUDY PARTICIPATION

The VERAFEYE System is similar in technology and indication to existing commercially available ICE systems, such as UltraICE (Boston Scientific), AcuNav and Soundstar (Biosense Webster), ViewFlex (Abbott). ICE systems provide the operator with additional means of intra-operative guidance such as orientation within the heart, and evaluating the size of the lumens. While there may be no direct benefit from participating in this study, because the VERAFEYE System provides real-time imaging, complications may potentially be detected earlier on.

**LUMINIZE_CLINICAL PROTOCOL**Document ID: VER-DOC-527
Controlled Document: VER-SIGN-3084TEMPLATE:
ONEPROJECTS/SIGN-267

Version: 4.0

Project: VERAFEYE (VER)
Date: 22-Nov-2024 14:16:10
Page: 34 / 51

The data collected in this clinical investigation will serve as critical input for VERAFEYE imaging technology improvement, as well as for the novel features development in future device releases. In this regard, the proposed clinical investigation is a pivotal step toward the development of next-generation intraoperative 4D-imaging devices, aimed to improve outcomes for future patients undergoing catheter ablation and structural heart procedures.

5.12. STATISTICAL DESIGN AND ANALYSIS

Given the nature of this feasibility study, analysis of study data will use descriptive statistical methods. The Sponsor shall use the imaging data for product development purposes only. Study data will be summarized and included in a clinical study report at the conclusion of the study enrolment.

5.13. SAFETY REPORTING**5.13.1. REPORTABLE EVENTS**

The investigator is responsible for documenting and reporting any of the following events to the study Sponsor:

- All Investigational Device Deficiencies
- All Serious Adverse Events
- Unanticipated Adverse Device Effects and Unanticipated Serious Adverse Device Effects
- All Thromboembolic Events
- All Device Related Adverse Events
- All Procedure Related Adverse Events
- New findings/updates in relation to already reported events

Definitions of reportable events are included in the Table below.

Table 6: Reportable Events Definitions

Term	Definition
Adverse Event	
Any untoward medical occurrence, unintended disease or injury, or any untoward clinical signs (including an abnormal laboratory finding) in subjects, users or other persons, in the context of a clinical investigation, whether or not related to the investigational medical device and whether anticipated or unanticipated.
 
NOTE 1: This includes events related to the investigational medical device or comparator.
 
NOTE 2: This definition includes events related to the procedures involved.

**LUMINIZE_CLINICAL PROTOCOL**Document ID: VER-DOC-527
Controlled Document: VER-SIGN-3084TEMPLATE:
ONEPROJECTS/SIGN-267

Version: 4.0

Project: VERAFYE (VER)
Date: 22-Nov-2024 14:16:10
Page: 35 / 51

Term	Definition
	
NOTE 3: For users or other persons, this definition is restricted to events related to the investigational medical device.

Adverse Device Effect	
Adverse event related to the use of an investigational medical device
 
NOTE 1: This includes any adverse event resulting from insufficiencies or inadequacies in the instructions for use, the deployment, the implantation, the installation, the operation, or any malfunction of the investigational medical device.
 
NOTE 2: This definition includes any event resulting from use error or from intentional misuse of the investigational medical device.
 
NOTE 3: This includes 'comparator' if the comparator is a medical device.

Serious Adverse Event	
Adverse event that led to any of the following:
 
death,serious deterioration in the health of the subject, users or other persons as defined by either:
a life-threatening illness or injury, ora permanent impairment of a body structure or a body function, including chronic diseases, orin-patient hospitalization or prolongation of existing hospitalization, ormedical or surgical intervention to prevent life-threatening illness or injury or permanent impairment to a body structure or a body functionfetal distress, fetal death, or a congenital abnormality or birth defect including physical or mental impairment. 
NOTE 1: Planned hospitalization for a pre-existing condition, or a procedure required by the clinical investigational plan, without a serious deterioration in health, is not considered a serious adverse event.

Serious Adverse Device Effect (SADE)	Adverse device effect that has resulted in any of the consequences characteristic of a serious adverse event.

**LUMINIZE_CLINICAL PROTOCOL**Document ID: VER-DOC-527
Controlled Document: VER-SIGN-3084TEMPLATE:
ONEPROJECTS/SIGN-267

Version: 4.0

Project: VERAFYE (VER)
Date: 22-Nov-2024 14:16:10
Page: 36 / 51

Term	Definition
Unanticipated Adverse Device Effect	Any serious adverse effect on health or safety or any life-threatening problem or death caused by, or associated with, a device, if that effect, problem, or death was not previously identified in nature, severity, or degree of incidence in the investigational plan or application (including a supplementary plan or application), or any other unanticipated serious problem associated with a device that relates to the rights, safety, or welfare of subjects.
Unanticipated Serious Adverse Device Effect	Serious adverse device effect which by its nature, incidence, severity, or outcome has not been identified in the current risk assessment. NOTE 1: Anticipated serious adverse device effect (ASADE) is an effect which by its nature, incidence, severity or outcome has been identified in the risk assessment.
Serious Health Threat	Signal from any adverse event or device deficiency that indicates an imminent risk of death or a serious deterioration in the health in subjects, users or other persons, and that requires prompt remedial action for other subjects, users or other persons. NOTE 1: This would include events that are of significant and unexpected nature such that they become alarming as a potential serious health hazard or possibility of multiple deaths occurring at short intervals.
Device Deficiency	An inadequacy of a medical device related to its identity, quality, durability, reliability, usability, safety or performance. NOTE 1: Device deficiencies include malfunctions, use errors, and inadequacy in the information supplied by the manufacturer including labelling. NOTE 2: This definition includes device deficiencies related to the investigational medical device [or the comparator].

5.13.2. REPORTING REQUIREMENTS**5.13.2.0.1. Investigator Reporting Requirements to Sponsor**

All reportable events experienced by study participants must be reported if they occur after the point of enrolment as defined in the subject classification section. Pre-existing conditions should not be reported as adverse events unless they worsen in severity or increase in frequency.

**LUMINIZE_CLINICAL PROTOCOL**Document ID: VER-DOC-527
Controlled Document: VER-SIGN-3084TEMPLATE:
ONEPROJECTS/SIGN-267

Version: 4.0

Project: VERAFYE (VER)
Date: 22-Nov-2024 14:16:10
Page: 37 / 51

Adverse events and device deficiencies must always be reported to the Sponsor through the CRFs. Completed CRFs are to be sent to the following email address of the sponsor:

[contact]

Reporting timelines are included in Table 7 below.

Table 7: Investigator Reporting Requirements

Event Classification	Communication Method	Communication Timeline pre-market studies
Unanticipated Adverse Device Effect / Unanticipated Serious Adverse Device Effect	Complete AE CRF page with all available new and updated information.	
Within 1 business day of first becoming aware of the event.Terminating at the end of the study
	Provide all relevant source documentation (de-identified/pseudonymized) for reported event, as requested by sponsor.	
Upon request of sponsor.
Serious Adverse Event	Complete AE CRF page with all available new and updated information.	
Within 3 calendar days of first becoming aware of the event or as per local/regional regulations.Reporting required through the end of the study
	Provide all relevant source documentation (de-identified/pseudonymized) for reported event.	
Upon request of sponsor

**LUMINIZE_CLINICAL PROTOCOL**Document ID: VER-DOC-527
Controlled Document: VER-SIGN-3084TEMPLATE:
ONEPROJECTS/SIGN-267

Version: 4.0

Project: VERAFYE (VER)
Date: 22-Nov-2024 14:16:10
Page: 38 / 51

Event Classification	Communication Method	Communication Timeline pre-market studies
Serious Adverse Device Effects	Complete AE CRF page with all available new and updated information.	
Within 3 calendar days of first becoming aware of the event or as per local/regional regulations.Reporting required through the end of the study
	Provide all relevant source documentation (de-identified/pseudonymized) for reported event.	
When documentation is availableAt sponsor request.
Device Deficiencies (including but not limited to failures, malfunctions, and product nonconformities)	Complete Device Deficiencies CRF with all available new and updated information.	
Within 3 calendar days of first becoming aware of the event.Reporting required through the end of the study
	Provide all relevant source documentation (de-identified/pseudonymized) for reported event.	
Upon request of sponsor
Adverse Event including Adverse Device Effects	Complete AE CRF page, which contains such information as date of AE, treatment of AE resolution, assessment of seriousness and relationship to the device.	
In a timely manner after becoming aware of the informationReporting required through end of study
	Provide all relevant source documentation (de-	
Upon sponsor request

**LUMINIZE_CLINICAL PROTOCOL**Document ID: VER-DOC-527
Controlled Document: VER-SIGN-3084TEMPLATE:
ONEPROJECTS/SIGN-267

Version: 4.0

Project: VERAFYE (VER)
Date: 22-Nov-2024 14:16:10
Page: 39 / 51

Event Classification	Communication Method	Communication Timeline pre-market studies
	identified/pseudonymized) for reported event, as requested by sponsor.	

All events will be assessed by the investigator for relationship to study device and the study procedure.

Table 8: Relationship Events to Procedure/Device

Classification	Description
Not Related	
Relationship to the device, comparator or procedures can be excluded when:
 
 - the event has no temporal relationship with the use of the investigational device or the procedures related to the use of the investigational device; - the serious event does not follow a known response pattern to the medical device (if the response pattern is previously known) and is biologically implausible; - the discontinuation of medical device application or the reduction of the level of activation/exposure - when clinically feasible – and reintroduction of its use (or increase of the level of activation/exposure), do not impact on the serious event; - the event involves a body-site or an organ that cannot be affected by the device or procedure; - the serious event can be attributed to another cause (e.g. an underlying or concurrent illness/ clinical condition, an effect of another device, drug, treatment or other risk factors); - the event does not depend on a false result given by the investigational device used for diagnosis, when applicable;

**LUMINIZE_CLINICAL PROTOCOL**Document ID: VER-DOC-527
Controlled Document: VER-SIGN-3084TEMPLATE:
ONEPROJECTS/SIGN-267

Version: 4.0

Project: VERAFYE (VER)
Date: 22-Nov-2024 14:16:10
Page: 40 / 51

Classification	Description
	In order to establish the non-relatedness, not all the criteria listed above might be met at the same time, depending on the type of device/procedures and the serious event.
Possibly Related	The relationship with the use of the investigational device or comparator, or the relationship with procedures is weak but cannot be ruled out completely. Alternative causes are also possible (e.g. an underlying or concurrent illness/ clinical condition or/and an effect of another device, drug or treatment). Cases where relatedness cannot be assessed or no information has been obtained should also be classified as possible.
Probably Related	The relationship with the use of the investigational device or comparator, or the relationship with procedures seems relevant and/or the event cannot be reasonably explained by another cause.
Causal Relationship	
The serious event is associated with the investigational device or comparator or with procedures beyond reasonable doubt when:
 
- the event is a known side effect of the product category the device belongs to or of similar devices and procedures;- the event has a temporal relationship with investigational device use/application or procedures;- the event involves a body-site or organ that-the investigational device or procedures are applied to;-the investigational device or procedures have an effect on;- the serious event follows a known response pattern to the medical device (if the response pattern is previously known);- the discontinuation of medical device application (or reduction of the level of activation/exposure) and reintroduction of its use (or increase of the level of activation/exposure), impact on the serious event (when clinically feasible);- other possible causes (e.g. an underlying or concurrent illness/ clinical condition or/and an effect of another device, drug or treatment) have been adequately ruled out;- harm to the subject is due to error in use;

**LUMINIZE_CLINICAL PROTOCOL**Document ID: VER-DOC-527
Controlled Document: VER-SIGN-3084TEMPLATE:
ONEPROJECTS/SIGN-267

Version: 4.0

Project: VERAFYE (VER)
Date: 22-Nov-2024 14:16:10
Page: 41 / 51

Classification	Description
	
- the event depends on a false result given by the investigational device used for diagnosis, when applicable;
 
In order to establish the relatedness, not all the criteria listed above might be met at the same time, depending on the type of device/procedures and the serious adverse event.

